#### **5.4 Demography and Other baseline characteristics**

All demographic and baseline characteristics summaries and listings will be provided for the FAS/SAS. The summary will be repeated on the PP set if  $\geq 10\%$  of participants are excluded from the FAS/SAS. [Note: Demographic variables of age and sex will be collected in Study CLIN-60120-452, all other variables will be transferred from the parent study database]

Following descriptive summaries will be provided:

- Demographic variables (age, age categories [ $<15$ ,  $15-25$  &  $>25$ ] and EudraCT age categories, sex, race, ethnicity, height (cm), weight (kg) and BMI ( $\text{kg}/\text{m}^2$ )). See appendix A6 for defined EudraCT age categories
- Disease history (time since date of diagnosis by a physician (years), method of diagnosis and type of FOP genetic mutation)
- Flare-up history over the past 12 months prior to the Inclusion Visit (number of flare-ups, start and stop date of flare-ups, location of flare-ups, symptoms of flare-up, cause of flare-up and time since last flare-up (months)).
- Extra bone growth history over the past 6 months prior to the Inclusion visit (number of extra bone growths, locations, preceded by and symptoms)
- Bone maturity history, for participants aged  $<18$  years at study inclusion, (bone age, difference between chronological age and bone age (months), hand/wrist and knee epiphyseal assessment and skeletally mature assessments)

Time since date of diagnosis is defined as (Date of the first IMP administration of palovarotene in Study CLIN-60120-452 - date of diagnosis).

Date of diagnosis is collected directly for study PVO-1A-301. For PVO-1A-202/PVO-1A-204, age at first confirmation of heterotopic ossification (years) will be considered equivalent to the age of diagnosis and as such in combination with the birth date used to derive the year of the equivalent date of diagnosis.

[Note: 1 year = 365.25 days and 1 month = 30.4375 days].

Difference between chronological age and bone age is defined as (bone age – estimated age at time of bone maturity assessment [age captured at the inclusion visit will be used to calculate the year of birth, from which age at time of bone maturity assessment will be estimated by imputing the day and month as 30th June]).

Listings will also be provided for all the summaries listed above.

#### **5.5 Non-drug therapies, medications and surgical procedures**

Non-drug therapies and surgical procedures will be coded using the latest version of Medical Dictionary for Regulatory Activities (MedDRA) in effect within IPSEN at the time of database lock. Medications will be coded using the latest version of World Health Organization-Drug dictionary at the time of database lock. [Note: Prior medications will not be collected in Study CLIN-60120-452 but transferred from the final parent study database]

Medication, non-drug therapies and surgical procedures start and stop dates will be compared to the date of the first IMP administration of palovarotene in Study CLIN-60120-452 to allow classification as either Prior only, Prior and Concomitant, or Concomitant only:

Prior (P)	Start and stop dates prior to the date of the first IMP administration of palovarotene in Study CLIN-60120-452.
Prior and Concomitant (PC)	Start date before the date of the first IMP administration and stop date on or after the date of the first IMP administration of palovarotene in Study CLIN-60120-452.
Concomitant (C)	Start date on or after the date of first IMP administration of palovarotene in Study CLIN-60120-452.

Summary tables on prior medications/will include “P” only, summary tables on concomitant medications/non-drug therapies/surgical procedures will include “C” and “PC”. See detailed rules in appendix A3 for classification of prior and concomitant medication/non-drug therapies, surgical procedures in case of partial/missing date.

Following summaries, presenting count and percentages of participants will be provided on the enrolled set:

- Prior medications (P) by ATC class level 2 and Preferred Name,
- Concomitant medications (PC, C) by ATC class level 2 and Preferred Name
- Concomitant procedures (PC, C) by primary SOC and Preferred Term,

Listings will be provided for all the summaries listed above. These listings should include a flag indicating the category (P, PC and C) as described in the table above.

## 5.6 Compliance

Compliance is defined as (total actual doses taken/total expected doses taken) x 100.

The total actual dose taken will be calculated as (total [capsules dispensed to the participant x respective dosage] – total [capsules returned x respective dosage]) by the participant across all medication kits dispensed.

If the number of returned capsules is missing from any kit, the number of returned capsules for that kit will be imputed by multiplying the number of capsules dispensed by the mean compliance observed in the MOVE study. For chronic kits (or weight-adjusted/de-escalate equivalent)  $\leq 5$ mg, a compliance of 80% will be used estimate the number of capsules returned. For flare-up kits (or weight-adjusted/de-escalate equivalent)  $> 5$ mg, a compliance of 87% will be used to estimate the number of capsules taken for that kit. These imputed values will then be used to determine the overall dose taken across the duration of the study.

The total expected dose taken will be calculated by multiplying the duration of treatment in days for each treatment regimen, across all cycles of that regimen, (see derivation under section 5.6.6) by the planned dose for each regimen and finally totalling the expected dose across all regimens.

The expected duration of treatment is calculated as following for each treatment regimen:

Total of expected regimen cycle dosing periods across all regimen cycles. Each expected regimen cycle dosing period is defined as (last regimen cycle dose date – first regimen cycle dose date + 1).

Compliance will be summarised for the FAS/SAS set with descriptive statistics. Compliance in each category (<80%, ≥80% - ≤120%, >120%) will also be summarised for counts and percentages of participants.

A listing of treatment compliance, including all derived parameters will be provided.

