Route of Administration	Oral
Use	Active study intervention
IMP and NIMP/AMP.	IMP
Sourcing	Centrally by sponsor

Packaging and Labelling	
Study intervention will be provided in bottle or blister packaging:
 
 - 90 capsules packaged in a bottle (1 mg, 1.5 mg, 2.5 mg, 5 mg and 10 mg). - 14 capsules packaged in a blister (1 mg, 1.5 mg and 5 mg) - 15 capsules packaged in a bottle (5 mg) for US patients only. 
Each carton will be labelled as required per country requirement.

Storage requirements	To be stored at room temperature (between 15°C and 30°C) and protected from light and humidity.
Former Names/Alias(es)	None

AMP=auxiliary medicinal product; FOP= fibrodysplasia ossificans progressiva; IMP=investigational medicinal product; NIMP=non investigational medicinal product.

Participants will be instructed to report potential flare-up symptoms to study site personnel. Only one symptom is required to define a flare-up. If these symptoms are consistent with previous flare-ups, include a participant-reported onset date, and are confirmed by the investigator as associated with a flare-up, participants will immediately begin flare-up-based treatment. Flare-up based treatment should also be initiated if the investigator confirms the presence of a substantial high-risk traumatic event likely to lead to a flare-up.

Based on clinical signs and symptoms as determined by the investigator, flare-up treatment may be extended in 4-week intervals while on-treatment with 10 mg palovarotene and continue until the flare-up resolves and the 4-week extension treatment has been completed.

Participants will be supplied with chronic treatment as well as the appropriate dose of palovarotene to initiate flare-up treatment when a flare-up or traumatic event is confirmed by the investigator (during in-clinic or remote visit, or by telephone contact).

Participants will be instructed to contact study site personnel immediately in case of intolerable adverse reactions during palovarotene treatment. The investigator will assess the adverse reaction and, if appropriate, will instruct the participant to reduce the daily dose of palovarotene as described in Section 6.5. If the participant does not have the appropriate dose in his/her possession, the study site will make immediate arrangements to ship the appropriate palovarotene dose to the participant.

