6.4 Study Intervention Administration/Accountability

Study intervention bottles and blisters will be brought back to the site and accountability performed. Accountability will be documented in the source documents and IWRS.

A record of the quantity of palovarotene dispensed to and administered by each participant must be maintained and reconciled with study intervention and accountability records.

Palovarotene status (treated or not treated) and regimen (chronic or flare-up or intercurrent flare-up or persistent flare up symptoms treatment) at the time of transition to Study CLIN-60120-452 will be collected at the Inclusion Visit.

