#### 5.8.2 *Extent of exposure*

Duration of total treatment, duration of flare-up treatment, mean duration of flare-up treatment and duration of chronic treatment will be summarised for the FAS/SAS with descriptive statistics. In the eCRF Dosing Form, for each treatment period, only the start date if completed (no end date). So, for each period, the end date will be considered as the start date of the following period (periods have to be sorted by start date) – 1. For the last record, it will be the date of last dose if collected, or if not the date of last contact. The date of last contact will be the latest date available across all assessments.

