##### 5.8.2.1 *Total Duration of Treatment*

Total duration of treatment is defined as (last dose date of IMP administration of palovarotene in Study CLIN-60120-452 - first dose date of IMP administration of palovarotene in Study CLIN-60120-452 + 1). The first dose date will be the start date of the first record in eCRF Dosing Form and the last dose date will be the date of last contact.

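### Three SAP derivations give wrong compliance or exposure values under specific triggers: a missing return count (5.6), a dated contact after the last dose (5.8.2.1), and out-of-span or interrupted flare-up cycles (5.8.2.3)

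*SAP*

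**What the plan says.** **Compliance (SAP 5.6).** Dose taken is dispensed minus returned, weighted by capsule strength. For a kit without a return count, the general sentence says that "the number of returned capsules for that kit will be imputed by multiplying the number of capsules dispensed by the mean compliance", with the mean taken from the MOVE study. Two specific sentences follow. For chronic kits, "a compliance of 80% will be used estimate the number of capsules returned". For flare-up kits, "a compliance of 87% will be used to estimate the number of capsules taken for that kit". The section also refers to a section 5.6.6, which the SAP does not contain.

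**Total duration (SAP 5.8.2.1).** The formula runs from first to last dose, but the section then adds that "the last dose date will be the date of last contact". The parent section 5.8.2 has a different rule for the end of the last dosing record: "it will be the date of last dose if collected, or if not the date of last contact". It also says: "The date of last contact will be the latest date available across all assessments".

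**Chronic duration (SAP 5.8.2.3).** The formula is last chronic date minus first chronic date, minus flare-up duration, minus interrupted non-flare-up days, plus 1. Flare-up duration (5.8.2.2) is summed over all cycles after interrupted flare-up days have been removed.

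**The concern.** Each derivation works in the simple case and fails under a trigger that the plan itself foresees.

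- **Missing return count.** Compliance is the share taken, so multiplying it by capsules dispensed gives capsules taken, not returned. The participant can land in the wrong compliance category.
- **Dated contact after the last dose.** The protocol plans 30 days of safety follow-up (4.1) and, for women, a pregnancy test one month after stopping (8.2.6). If either is dated in the database, days off drug count as treatment.
- **Flare-up cycle outside the chronic span.** Three protocol pathways lead there: entering the study on flare-up treatment (6.1), moving from chronic to flare-up-only treatment (Table 4), and reaching the end of study during a flare-up course with no study drug afterwards (4.4, 6.6).
- **Interrupted days inside a cycle.** These are removed from flare-up duration but not from the chronic span, so they end up counted as chronic days.

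At stake are the compliance summary and categories, two of the four exposure summaries in 5.8.2, and the related listings. Several of the wrong values look plausible and would not stand out in a table.

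**Working it through.** The plan gives no worked figure for any of these derivations, so there is nothing to reproduce. The SAP formulas are applied literally.

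**Inputs from the documents:** 80% and 87%, and category cut-offs of 80% and 120% (SAP 5.6); 90-capsule bottles, and "15 capsules packaged in a bottle (5 mg) for US patients only" (Protocol Table 4); an 84-day flare-up course (Protocol 6.1); 30 days of follow-up (Protocol 4.1).

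**Assumed for illustration:** the dosing days below and, for compliance, a chronic-only and otherwise fully adherent participant with 540 capsules dispensed and 540 expected.

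**1. Compliance**

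One 90-capsule kit without a return count:
- Chronic, general sentence: returned 90 × 0.80 = 72, so taken 18 (20%). Intended: returned 90 × 0.20 = 18, so taken 72 (80%).
- Flare-up, general sentence: returned 90 × 0.87 = 78.3, so taken 11.7. Specific sentence: taken 78.3.

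Let f be the share of capsules without a count. Compliance as written is 100 × (1 − 0.8f); as intended it is 100 × (1 − 0.2f).

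| Capsules without a count | As written | Intended |
|---|---|---|
| 15 | (525 + 3)/540 = 97.8% | (525 + 12)/540 = 99.4% |
| 90 | (450 + 18)/540 = 86.7% | (450 + 72)/540 = 96.7% |
| 180 | (360 + 36)/540 = 73.3% | (360 + 144)/540 = 93.3% |

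The participant drops below 80% when 1 − 0.8f < 0.80, that is, f > 0.25. Under the intended rule the lowest value, at f = 1, is exactly 80%.

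Reversing the rule is not enough by itself. Participants also hold flare-up supply that they may never start (Protocol 6.1). An unused kit of 90 × 10 mg without a count would be imputed as 90 × 10 × 0.87 = 783 mg taken. Against 365 × 5 = 1825 mg expected, this adds 42.9 points and moves a fully adherent participant to 142.9%, in the >120% category.

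**2. Total duration**

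First dose Day 1, last dose Day 365, last contact Day 395:
- As written: 395 − 1 + 1 = 395. With the last dose date: 365.
- Chronic duration for the same chronic-only participant: 365 − 1 − 0 + 1 = 365, so the two durations disagree within one summary.

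A 30-day gap is 30/365.25 = 8.2% at 12 months and 30/1095.75 = 2.7% at 36 months. The gap is 0 if the EOS/EW Visit, which is placed at last intake, is the last dated contact.

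**3. Chronic duration** (last − first − flare-up days − non-flare-up interruptions + 1)

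| Pattern | As written | True |
|---|---|---|
| Chronic Days 1–100 and 185–365; flare-up 101–184, no interruption | 365 − 1 − 84 + 1 = 281 | 100 + 181 = 281 |
| Same, 10 flare-up days interrupted | 365 − 1 − 74 + 1 = 291 | 281 |
| 60 flare-up days, then chronic Days 61–400 | 400 − 61 − 60 + 1 = 280 | 340 |
| Chronic Days 1–300, then 60 flare-up days to EOS | 300 − 1 − 60 + 1 = 240 | 300 |
| Chronic Days 1–100, then flare-up only, one 84-day cycle | 100 − 1 − 84 + 1 = 16 | 100 |
| Same, two cycles | 100 − 1 − 168 + 1 = −68 | 100 |

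The formula is right only when every cycle lies inside the span and none has interrupted flare-up days. The opening premise of 5.8.2.3, that chronic treatment runs from the first chronic dose, suggests that earlier cycles were not meant to be deducted. The formula carries no such limit, and the premise does not deal with cycles after the last chronic date.

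**The case against.** The strongest reply has four parts.

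- **The outputs are descriptive.** This is true and limits the scope. But describing compliance and exposure is all these tables do, so a wrong value defeats their purpose.
- **The intent can be recovered.** The flare-up sentence in 5.6 uses the right direction, the chronic sentence taken alone could be read either way, and 5.8.2 already has the right order of dates. This also stands: 20% taken is what the general sentence gives, not a certain programmed result. A programmer still has conflicting instructions to choose between.
- **The triggers may be rare.** The protocol requires that "Study intervention bottles and blisters will be brought back to the site and accountability performed", and a category change in the compliance example needs more than a quarter of the capsules uncounted. The schedule of activities has no post-treatment visit column. This stands too, but the SAP expects some missing counts, since it writes a rule for them.
- **Impossible values would be noticed.** That holds for −68, but not for 16, 240 or 291.

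A reader might infer that the primary safety results are compromised. The documents do not support that. The TEAE window in 5.7.2.2 uses the last dose date, with last contact only as fallback. The AE summaries are participant counts, percentages and event counts, and the flare-up rates use time from consent to end of study. Nor can an effect on the Per Protocol Set be claimed, because its exclusion rules are in a Protocol Deviation Plan that is not among the documents.

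**Conclusion.** The point holds, within limits. Three derivations give wrong descriptive values when their triggers occur:

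- **Compliance:** a chronic kit without a count scores 20% instead of 80% taken under the general sentence; a flare-up kit scores 13% or 87%, depending on the sentence followed.
- **Total duration:** overstated by the gap between last dose and last contact, taken here as 0 to 30 days, or 0 to 8.2% at 12 months.
- **Chronic duration:** understated by the flare-up days outside the chronic span, and overstated by the interrupted flare-up days inside it.

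Two stronger readings of 5.8.2.3 should be avoided. It is not wrong for everyone who has a flare-up, since an uninterrupted in-span cycle gives the correct 281 days. Nor is an in-span cycle always safe, as 291 against 281 shows. That last figure takes the interruption term to mean breaks in chronic dosing outside flare-up cycles. If it also covered flare-up days, on which chronic drug is stopped anyway, those days would be deducted twice.

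Flare-up duration and mean flare-up duration are not affected by these three defects. The number of participants affected cannot be known from the documents. The correction should be made before database lock.

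**What to change.** 1. **SAP 5.6.** Impute capsules returned as dispensed × (1 − compliance), with 0.80 for chronic and 0.87 for flare-up kits, worded the same way in the general and both specific sentences. Apply it only to kits with evidence of use, such as a matching dosing record, and state how unstarted flare-up kits are handled.
2. **SAP 5.8.2.1.** Use the last dose date if collected, and last contact only if it is missing, as in 5.8.2.
3. **SAP 5.8.2.3.** Sum the lengths of the chronic dosing records using the period rule in 5.8.2, excluding interrupted (0 mg) periods. SAP 5.7.2.2 already provides for 0 mg records. Restricting the deduction to in-span flare-up days is not enough unless interrupted days within those cycles are removed as well.
4. **Clerical.** Correct the reference to 5.6.6.

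The cost is SAP wording and small programming changes before database lock. The capsule counts, dosing-form records and last dose date are already named in the SAP, so no new data are needed.

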6.5 Dose Modification

Participants will be instructed to contact study site personnel immediately in case of intolerable adverse reactions during palovarotene treatment. The investigator will assess the adverse reaction and, if appropriate, will instruct the participant to reduce the daily dose to the next lower dosage as shown in [Table 5](#); additional dose reduction should occur if adverse reactions continue to be intolerable. If the participant is already receiving the lowest possible dose, then consideration should be given to discontinue therapy temporarily or permanently or switching

to flare-up treatment only (see Section 6.1). Subsequent flare-up treatment should be initiated at the same reduced treatment that was tolerated previously.

Table 5 Dose Reduction of Palovarotene

Dose Prescribed	Reduced Dose
20 mg	15 mg
15 mg	12.5 mg
12.5 mg	10 mg
10 mg	7.5 mg
7.5 mg	5 mg
5 mg	2.5 mg
2.5 mg	1 mg

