**Chronic treatment:** oral palovarotene once daily, 5 mg, or at the dose received during participation in the parent study at the time of transition Study CLIN-60120-452 or prior to interrupting/stopping palovarotene treatment.

**Flare-up treatment:** increase in dose at the time of a flare-up (or substantial high risk traumatic event likely to lead to a flare-up) to 20 mg once daily for 4 weeks (28 days), followed by 10 mg once daily for 8 weeks (56 days) for a total of 12 weeks (84 days) even if symptoms resolve earlier.

Participants receiving flare-up treatment at the time of transition to Study CLIN-60120-452 will continue and complete the flare-up treatment as was planned in the parent study.

Flare-up treatment should begin at the onset of the first symptom indicative of a FOP flare-up or substantial high risk traumatic event likely to lead to a flare-up. Chronic treatment should cease at the time of initiation of flare-up treatment, re-initiation of the chronic daily treatment should occur after completion of the flare-up treatment.

**Persistent flare-up symptoms:** treatment may be extended in 4-week intervals with 10 mg palovarotene and continued until the flare-up symptoms resolve.

**Intercurrent flare-up:** if the participant experiences an intercurrent flare-up (new flare-up location or marked worsening of the original flare-up) at any time during the flare-up treatment, then the 12-week flare-up treatment should be restarted.

In the case of any intolerable adverse reactions, the daily dose of the chronic/flare-up regimen can be reduced.

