### 5.8.2.2 Duration of Flare-up Treatment

For participants receiving flare-up treatment, duration of flare-up treatment (days) is defined as total flare-up cycle dosing periods (days) across all flare-up cycles. This includes any days for which the participant is receiving persistent flare-up symptom or intercurrent flare-up treatment.

For a flare-up cycle, the flare-up cycle dosing period (days) is defined as days that participants received flare-up-based treatment and is calculated as (last dose date of the flare-up cycle – first date of the flare-up cycle – days where flare-up medications were not taken/interrupted during the flare-up cycle + 1).

The mean duration of flare up treatment is defined as the total duration of flare-up treatment (across all cycles) divided by the number of flare-up treatment cycles for each individual.

The duration of persistent flare-up symptom and intercurrent flare-up treatment will be calculated in a similar manner.

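### SAP 5.6 leaves the compliance denominator undefined for in-study dose reductions, instructed interruptions and the 20/10 mg flare-up schedule, so fully adherent participants can score outside 80-120%

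*SAP*

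**What the plan says.** SAP 5.6 gives the ratio: "Compliance is defined as (total actual doses taken/total expected doses taken) x 100". The numerator is in milligrams. It is capsules dispensed times strength, minus "total [capsules returned x respective dosage", summed over kits, so it follows whatever strengths were actually taken.

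The denominator takes the days in each regimen over all its cycles, multiplies them "by the planned dose for each regimen and finally totalling the expected dose across all regimens". Each cycle's length is printed as "last regimen cycle dose date – first regimen cycle dose date + 1". For the day count the text says "see derivation under section 5.6.6", but SAP 5.6 has no subsections. Participants are then counted as below 80%, 80-120% or above 120%.

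Three other places bear on this:

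- SAP 2.2 sets flare-up treatment at "20 mg once daily for 4 weeks (28 days), followed by 10 mg once daily for 8 weeks (56 days"). That is two dose levels within one regimen, and SAP 5.1.1.2 does not split regimens by dose step.
- Protocol 6.5 says that, for intolerable adverse reactions, the investigator, if appropriate, "will instruct the participant to reduce the daily dose to the next lower dosage" in Table 5. Protocol 7.1.3 keeps participants in the study during a temporary interruption, and Protocol 6.8 requires study drug to stop during certain concomitant treatments.
- SAP 5.8.2.2, on exposure, subtracts "days where flare-up medications were not taken/interrupted during the flare-up cycle". SAP 5.8.2.3 does the same for chronic treatment.

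**The concern.** The two halves of the ratio follow different rules. The numerator falls as soon as a participant is told to take less or to pause. Nothing in SAP 5.6 makes the denominator fall with it. De-escalated doses are mentioned only in the rule for missing capsule returns, which feeds the numerator. The gap is therefore present even when every kit is fully reconciled.

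Reductions and many interruptions follow intolerable adverse reactions. The compliance table could then partly reflect tolerability in a study whose primary objective is safety, and participants who did as instructed could be counted as under-compliant. With the planned dose undefined and the cross-reference dead, two programmers could also derive different denominators from the same text.

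**Working it through.** The SAP gives no worked compliance figure to reproduce, so the check applies its formula to hypothetical participants with perfect adherence (milligrams taken equal milligrams instructed).

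**Inputs.** Chronic dose 5 mg daily and flare-up course 28 days at 20 mg then 56 days at 10 mg (SAP 2.2). Reduction steps 20 to 15, 10 to 7.5 and 5 to 2.5 mg (Protocol Table 5). Follow-up spans of 182, 365 and 1095 days are illustrative; SAP 2.2 allows up to three years.

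**Formula.** Compliance = 100 × mg taken / sum over regimens of (days × planned dose).

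**1. Reduction during the study, planned dose left unreduced.**
- 5 to 2.5 mg halfway through 182 days: (91 × 5 + 91 × 2.5) / (182 × 5) = 682.5 / 910 = 75.0%.
- The same 91 reduced days within 365: (274 × 5 + 91 × 2.5) / (365 × 5) = 1597.5 / 1825 = 87.5%.
- For this step, the score is below 80% when 1 − 0.5f < 0.8, that is, when more than 40% of days are reduced.
- Flare-up course at 15/7.5 mg, against a denominator that does follow the 20/10 schedule: taken 28 × 15 + 56 × 7.5 = 840 mg; expected 28 × 20 + 56 × 10 = 1120 mg; 840 / 1120 = 75.0%.

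**2. Instructed interruption left in the day count (constant chronic dose).**
- 42 days off in 182: 140 / 182 = 76.9%.
- 42 days off in 365: 323 / 365 = 88.5%.
- 42 days off in 1095: 1053 / 1095 = 96.2%.
- The score falls below 80% once more than 20% of days are interrupted.

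**3. The 20/10 mg schedule.** A fully taken course is 1120 mg over 84 days. The result depends on what is used as the planned dose:

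| Planned dose used | Expected mg | Compliance |
|---|---|---|
| 20 mg on all 84 days | 1680 | 66.7% |
| 10 mg on all 84 days | 840 | 133.3% |
| 20 then 10 mg, as scheduled | 1120 | 100% |

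With chronic 5 mg on the other 281 days of a year, taken dose is 281 × 5 + 1120 = 2525 mg. The 20 mg reading gives 2525 / 3085 = 81.8% and the 10 mg reading gives 2525 / 2245 = 112.5%, both inside the band. Solving (5 + 8.33f) / (5 + 15f) = 0.8 and (5 + 8.33f) / (5 + 5f) = 1.2 shows that the band is left only when flare-up days exceed about 27% (20 mg reading) or 43% (10 mg reading) of treatment days.

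**After the fix.** With each day counted at its prescribed dose and instructed interruptions at zero, numerator and denominator agree and every case above scores 100%.

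**The case against.** Four points can be made for the plan.

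- **Flare-up dose.** A reader might infer that SAP 5.6 applies one dose to all 84 flare-up days. It does not say so. Applying the schedule in SAP 2.2 gives 100%, so 66.7% and 133.3% hold only under a reading that the SAP does not direct. This stands: for the flare-up schedule the fault is silence, not a wrong formula.
- **Entry dose.** A reader might infer that participants who entered on a lower individualised dose are mis-scored. SAP 2.2 defines chronic treatment as 5 mg or the dose carried over from the parent study, so for them the lower dose is the planned dose. Only reductions made during this study are at issue.
- **Exposure rules.** A reader might infer that SAP 5.6 contradicts SAP 5.8.2. Exposure rightly removes every day without drug. An expected dose should not, because removing self-chosen missed days would hide non-adherence. The difference is not in itself an error; what is missing is a rule for instructed interruptions.
- **Alternative readings and consequence.** If planned dose means the dose currently prescribed, and an interruption closes a cycle, the problem disappears. Neither term is defined, so this is possible but not stated. Compliance is also one descriptive table, the SAP promises a listing of all its derived parameters, and adverse events leading to dose change are tabulated separately. These limit the consequence but do not supply the missing definition.

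**Conclusion.** The point holds for in-study reductions and instructed interruptions. Taking the printed cycle length and an unreduced planned dose, a fully adherent participant scores 75.0% or 76.9% in the short-span examples. For the 20/10 mg schedule the SAP is incomplete, and the size of any error depends on the reading chosen.

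The effect is moderate. Constant-dose chronic participants score 100%, and longer follow-up brings many cases back into the band. The documents give no rate of reductions or interruptions in this study, so the number misclassified cannot be estimated. A reader might infer that the Per Protocol Set is affected. The documents show no such link, because the exclusion rules sit in a separate Protocol Deviation Plan. The point should be settled before database lock, but it does not touch the primary or secondary endpoints.

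**What to change.** In SAP 5.6, define expected dose as the sum over dosing-form records of prescribed daily dose on the record times days in the record, using the period end dates in SAP 5.8.2. The 20 mg phase, the 10 mg phase and each instructed reduction then count at their prescribed dose.

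Give zero expected dose only to interruptions instructed by the investigator or required by the protocol, and keep self-chosen missed days in the denominator. Correct the reference to 5.6.6. Pointing it to the durations in 5.8.2.2 and 5.8.2.3 would not do, because those remove all untaken days.

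First confirm that the dosing form holds the prescribed dose and the reason for any 0 mg period. The SAP shows only that it holds dose records, including 0 mg, with start dates. If it records dose taken, the denominator would approach the numerator and compliance would drift to 100% by construction.

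The cost is SAP wording and programming, plus that check. Compliance would then measure adherence to the prescribed dose, so dose intensity against the protocol dose needs its own line if wanted. No dose or clinical rule changes.
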